### 4.2 Pre-enrollment Phase

### 4.2.1 Screening Period (Visit 1)

During this period, subjects will be assessed for eligibility and have a platelet count performed.

The Screening Visit and Day 1 Baseline Visit platelet counts will be averaged to obtain the baseline platelet count value. The 2 samples must be obtained  $\geq$ 48 hours and  $\leq$ 2 weeks apart and the results must be available prior to enrollment. Therefore, an additional screening platelet count may be required due to issues with scheduling. If an additional platelet count is taken, an average of the last 2 platelet counts of  $\geq$ 48 hours apart must be  $<30\times10^9/L$  for eligibility. No single platelet count can be  $>35\times10^9/L$ .

Reasons for screen failure will be collected in the electronic case report form (eCRF).

### 4.3 Core Phase

# 4.3.1 Baseline Visit (Visit 2)

During this visit, baseline assessments, including platelet count, will be performed and avatrombopag administration will be started.

## 4.3.2 Dose and Dosage Titration Period (Visits 3 to 7)

During this period, dose, and dosage titration of avatrombopag from the initial starting dose will be performed in accordance with protocol-specified dose and dosage titration guidelines in order to find the minimum dose required to maintain platelet counts of  $\geq 50 \times 10^9/L$  and  $< 200 \times 10^9/L$ . No downward titration of concomitant ITP medication will be permitted during this period unless there is a safety concern. Subjects will return on Days 5, 8, 14, 21 and 28 during this period.

# 4.3.3 Concomitant ITP Medication Reduction Period (Visits 8 to 13)

During this period, downward titration of concomitant ITP medication will be permitted in accordance with the guidelines described in Section 6.5.3. This may require additional study drug dose and dosage adjustments before and after the concomitant ITP medication downward titration. Subjects will return every 2 weeks during this period.

### 4.3.4 Maintenance Period (Visits 14 to 22)

Subjects will continue treatment in order to maintain platelet counts of  $\geq 50 \times 10^9 / L$  and  $\leq 200 \times 10^9 / L$ . Study drug dose and dosage adjustments will be made in accordance with the dose and dosage titration guidelines. No downward titration of concomitant ITP medication will be permitted during this period unless there is a safety concern. Subjects will return weekly for visits.

At the EOT Visit (Visit 22), subjects will have the option to enter the Extension Phase and continue to receive avatrombopag. Subjects who are unable or unwilling to continue in the Extension Phase of the study will enter the Dose/dosage tapering and Follow-up Periods.

Subjects who require study drug dose adjustments, who undergo concomitant ITP medication reduction or who receive rescue therapy during the periods of Concomitant Medication Reduction and Maintenance Periods are required to return for weekly visits for 3 consecutive weeks.

## 4.3.5 Dose-tapering Period (Visits 23 to 26)

During this period, subjects who do not continue into the Extension Phase will be required to attend weekly visits at which the study drug will be down titrated 1 dose level per week until the study drug is discontinued. This can take up to 4 weeks (see Table 1). During the Dose-tapering Period, subsequent upward titration or addition of concomitant ITP medication should be considered, at the Investigator's discretion, to prevent the recurrence of thrombocytopenia. Once the dose tapering is complete, subjects will go directly to the Follow-up Visit (Visit 27).

# 4.3.6 Follow-up Period (Visits 27 to 30)

During this period, subjects will be followed for 4 weeks after the last dose taken in the Dose-tapering Period. Subjects will return approximately every week for visits during this period and will have their final evaluations on the last day of the Follow-up Period. Platelet counts will be carefully monitored during this period for the recurrence of thrombocytopenia.

Subsequent upward titration or addition of concomitant ITP medication should be considered, athe Investigator's discretion, to prevent the recurrence of thrombocytopenia.

### 4.4 Extension Phase

Those subjects who meet all the eligibility requirements for the Extension Phase and who are willing and able will enter the Extension Phase and can continue to receive avatrombopag in the Extension Phase until market authorization in Japan. Subjects entering directly into the Extension Phase will not enter the Dose-tapering and Follow-up Periods of the Core Study.

Safety and efficacy data will be collected monthly in the Extension Phase. Subjects who require study drug dose adjustments, who undergo concomitant ITP medication reduction, or who receive rescue therapy during the Extension Phase are required to return for weekly visits for 3 consecutive weeks.

## 4.5 Study Indication

The indication for this study is the treatment of chronic primary ITP in adults.

### 5 SELECTION AND WITHDRAWAL OF SUBJECTS

### 5.1 Inclusion Criteria

# **5.1.1** Primary Investigation Phase (Core Phase)

Subjects who meet all the following criteria will be eligible to participate in the Core Phase:

- 1. Men and women  $\geq$ 18 years of age.
- 2. Subject must be able to provide informed consent.
- 3. Subject has a confirmed diagnosis of chronic ITP (≥12 months duration) and has had an insufficient response to a previous ITP treatment, in the opinion of the Investigator.
- 4. Subject has an average of 2 platelet counts  $<30\times10^9/L$  (no single count can be  $>35\times10^9/L$ ). The 2 samples must be obtained  $\ge48$  hours and  $\le2$  weeks apart.

### **5.1.2** Extension Phase

1. No significant safety or tolerability concerns with the subject's participation in the Primary Investigation Phase (Core Phase) as determined by the Investigator.

### **5.2** Exclusion Criteria

## **5.2.1** Primary Investigation Phase (Core Phase)

Subjects who meet any of the following criteria will not be eligible to participate in the study:

- 1. Subjects with known secondary immune thrombocytopenia (e.g., with known *Helicobacter pylori*-induced ITP, subjects infected with known human immunodeficiency virus [HIV] or HCV or subjects with known systemic lupus erythematosus).
- 2. Subjects with known inherited thrombocytopenia (e.g., MYH-9 disorders) or hereditary thrombophilic disorders (e.g., Factor V Leiden, antithrombin III deficiency).
- 3. History of myelodysplastic syndrome (MDS).
- 4. History of arterial or venous thrombosis.
- 5. Subjects with a history of significant cardiovascular disease (e.g., congestive heart failure [CHF] New York Heart Association Grade III/IV, arrhythmia known to increase the risk of thromboembolic events [e.g., atrial fibrillation], angina, coronary artery stent placement, angioplasty, coronary artery bypass grafting).
- 6. Subjects with a history of cirrhosis, portal hypertension, or chronic active hepatitis.
- 7. Subjects with concurrent malignant disease or receiving cytotoxic chemotherapy for a reason other than ITP treatment.
- 8. Use of immunoglobulins (IVIg and anti-D) or corticosteroid rescue therapy within 1 week of Day 1/Baseline.
- 9. Splenectomy or use of rituximab within 12 weeks of Day 1/Baseline.
- 10. Use of romiplostim or eltrombopag within 1 week of Day 1/Baseline.

- 11. Use of chronic corticosteroid treatment or azathioprine within 4 weeks of Day1/Baseline, unless receiving a stable dose for at least 4 weeks.
- 12. Use of mycophenolate mofetil, cyclosporin A, or danazol within 4 weeks of Day1/Baseline, unless receiving a stable dose for at least 12 weeks.
- 13. Use of cyclophosphamide or vinca alkaloid regimens within 4 weeks of Baseline Visit.
- 14. Currently receiving moderate or strong dual inhibitors/inducers of CYP2C9 and CYP3A4 (see Appendix D for examples).
- 15. Serum creatinine  $\geq 1.5 \times$  the upper limit of normal (ULN).
- 16. Serum bilirubin ≥2×ULN.
- 17. Alanine aminotransferase (ALT) or aspartate aminotransferase (AST)  $\geq 3 \times ULN$ .
- 18. Females who are pregnant (positive beta-human chorionic gonadotropin positive [β-hCG] test) or breastfeeding.
- 19. Known allergy to avatrombopag or any of its excipients.
- 20. Received treatment with an investigational drug within 30 days or 5 half-lives (whichever is longer) before Day 1/Baseline.
- 21. Any clinically relevant abnormality which makes the subject unsuitable for participation in the study, in the opinion of the Investigator.
- 22. Considered unable or unwilling to comply with the study protocol requirements.

#### **5.2.2** Extension Phase

- 1. Subjects for whom participation in the Extension Phase is considered inappropriate, based on the Investigator's judgment.
- 2. Subjects considered unable or unwilling to comply with the study protocol requirements, as determined by the Investigator.

### 5.3 Withdrawal Criteria

Participation of a subject in this clinical study may be discontinued for any of the following reasons:

- The subject withdraws consent or requests discontinuation from the study for any reason
- Occurrence of any medical condition or circumstance that exposes the subject to substantial risk and/or does not allow the subject to adhere to the requirements of the protocol
- Subject non-compliance or unwillingness to comply with the procedures required by the protocol
- Subject failed to meet inclusion/exclusion criterion

- Any SAE, clinically significant AE, severe laboratory abnormality, intercurrent illness, or other medical condition which indicates to the Investigator that continued participation is not in the best interest of the subject
- Pregnancy
- Investigator discretion
- Sponsor request
- Subject requires prohibited concomitant medication
- Termination of the study by the Sponsor or the regulatory authority

If a subject withdraws prematurely from the study due to the above criteria or any other reason, study staff should make every effort to complete the EOT assessments for the applicable phase. The reason for subject withdrawal must be documented in the eCRF.

In the case of subjects lost to follow-up, attempts to contact the subject must be made and documented.

If a subject is early terminated from the study, the EOT procedures should be performed. Subjects early terminated from the study will not be replaced, regardless of the reason for early termination.

# 5.3.1 Subjects with Study Drug Discontinuation

In both the Primary Investigation Phase (Core Phase) and the Extension Phase, study drug may be permanently discontinued at the discretion of the Investigator due to safety reasons, at the request of the subject, or if any of the following occur:

- Platelet count remains <30×10^9/L after more than 3 weeks at the maximum dose level (Level 6) (subjects can be discontinued after 7 days of therapy at the maximum dose level if they have dangerously low platelet counts in the opinion of the Investigator)
- Subjects who require rescue therapy more than 3 times or continuous rescue therapy for more than 3 weeks
- Excessive platelet count responses (> $400 \times 10^9$ /L) at the minimum dose level (Level 1)
- Treatment with certain ITP therapies/procedures, such as vinca alkaloids, cyclophosphamide, rituximab, splenectomy, or other TPO-RAs (eltrombopag, romiplostim).

If a subject discontinues study drug due to an AE, the Investigator will attempt to follow the event until it has resolved or stabilized.

If possible, a subject who discontinues treatment will complete the EOT assessments for the applicable phase and protocol-specified information will be collected. The primary reason for discontinuation and all other reason(s) contributing to the subject's discontinuation from study drug(s) as well as the date of last dose should be collected in the CRF.

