## 6.4.4 Study Drug Dose-Adjustment Guidelines

In accordance with approved overseas labeling, dose and dosage adjustments will target maintaining the platelet count  $\geq 50 \times 10^9 / L$  and  $< 200 \times 10^9 / L$  and follow the dose-adjustment guidelines presented in Table 1 and Table 2. All subjects will initiate treatment at 20 mg once daily (Dose Level 4).

Investigators must consider dose and dosage titration in accordance with a subject's platelet count every 2 weeks. However, dose titration may be performed weekly for subjects with platelet counts  $<50\times10^9/L$  or  $>400\times10^9/L$ .

**Table 1** Avatrombopag Dose Levels for Titration

Dose*	Level
40 mg Once Daily	6
40 mg Three Times a Week AND 20 mg on the Four Remaining Days of Each Week	5
20 mg Once Daily	4
20 mg Three Times a Week	3
20 mg Twice a Week OR 40 mg Once Weekly	2
20 mg Once Weekly	1

\* Subjects taking avatrombopag less frequently than once daily should take the medication in a consistent manner from week to week.

**Table 2** Avatrombopag Dose Adjustments

Platelet Count (× 10  /L)	Dose Adjustment or Action
<50 after at least 2	Increase One Dose Level per Table 1.
weeks of Avatrombopag	• Wait 2 weeks to assess the effects of this regimen and any subsequent dose adjustments.
≥50 to <200	Keep on the current dose and dosage
≥200 to ≤400	Decrease One Dose Level per Table 1.
	• Wait 2 weeks to assess the effects of this regimen and any subsequent dose adjustments.
>400	Stop Avatrombopag.
	Increase platelet monitoring to twice weekly.
	• When platelet count is less than 150×10  /L, decrease One Dose Level per Table 1 and reinitiate therapy.
<50 after 4 weeks of 40 mg Avatrombopag once daily	Discontinue Avatrombopag.
>400 after 2 weeks of 20 mg Avatrombopag weekly	Discontinue Avatrombopag.

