#### 7.3 Extension Phase

# 7.3.1 Visits E1-E23/Months 1-23: Extension Phase (Monthly Visits)

Subjects should return to the clinic for monthly visits during the extension phase. Additional visits may be needed beyond 23 months if marketing authorization has not occurred. Subjects who require study drug dose adjustments, who undergo concomitant ITP medication reduction, or who receive rescue therapy during the Extension Phase are required to return for weekly visits for 3 consecutive weeks.

The following procedures should be performed at every visit:

- Collect vital signs (blood pressure and pulse) at each visit. Vital signs should be taken
  after sitting for 5 minutes whenever possible. Vital signs should be taken prior to any
  blood draws.
- Collect platelet counts via local lab.
- Perform WHO Bleeding Scale Assessment (Appendix C). The Investigator should ask the subject the following question: "Have you experienced any bruising or bleeding since the last visit?"
- Dispense study drug, if applicable, and review administration instructions at each visit.
- Retrieve unused medication, as needed, and review subject dosing diary to record compliance at every visit.
- Dispense new diary, if needed.
- Review and record AEs that may have occurred since the last visit.
- Record any use of rescue medication since the previous visit.
- Record concomitant medications and procedures.

The following procedures should be performed every three months starting at Visit E1/Month 1 in addition to the assessments performed at every visit:

- Collect blood for central laboratory tests (see Section 9.7).
- Perform pregnancy test for female subjects of childbearing potential.
- Perform physical exam.

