#### 7.3.2 Visit E24/Month24: End of Treatment

- Collect vital signs (blood pressure and pulse). Vital signs should be taken after sitting for 5 minutes whenever possible. Vital signs should be taken prior to any blood draws.
- Collect platelet counts via local lab.
- Collect blood for central laboratory tests (see Section 9.7).
- Perform pregnancy test for female subjects of childbearing potential- Urine or serum pregnancy test should be performed.

- Perform WHO Bleeding Scale Assessment (Appendix C). The Investigator should ask the subject the following question: "Have you experienced any bruising or bleeding since the last visit?"
- Perform physical exam.
- Retrieve unused medication and review subject dosing diary to record.
- Review and record AEs that may have occurred since the previous visit.
- Record any use of rescue medication since the previous visit.
- Record concomitant medications and procedures.

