# APPENDIX B: EXTENSION PHASE SCHEDULE OF EVENTS

Visits a	E1 - 2	Е3	E4-5	E6	E7-8	E9	E10-11	E12	E13-14	E15	E16-17	E18	E19-20	E21	E22-23	E24 or EOT	Unsch Visit b
Months c	1-2	3	4-5	6	7-8	9	10-11	12	13-14	15	16-17	18	19-20	21	22-23	24 or EOT	
Concomitant medications	X	X	X	X	X	X	X	X	X	X	X	X	X	X	X	X	X
Vital signs	X	X	X	X	X	X	X	X	X	X	X	X	X	X	X	X	X
Physical examination	X		$X^d$		X d		X d		$X^{d}$		$X^d$		$X^d$		$X^{d}$	X	
Dispense study drug and diary, as needed	X	X	X	X	X	X	X	X	Х	X	Х	X	Х	X	X		
Retrieve unused study medication and record compliance	X	X	X	X	X	X	X	X	X	X	X	X	X	X	X	X	
Platelet counts	X	X	X	X	X	X	X	X	X	X	X	X	X	X	X	X	X
Chemistry/ Hematology/ Coagulation	X		X d		X d		X d		X d		X d		X d		X d	X	
Pregnancy Test	X		X d		X d		X d		X d		X d		$X^d$		X d	X	
Adverse Events	X	X	X	X	X	X	X	X	X	X	X	X	X	X	X	X	X
WHO Bleeding	X	X	X	X	X	X	X	X	X	X	X	X	X	X	X	X	X

EOT = end-of-treatment, Unsch = unscheduled, WHO = World Health Organization.

a: Subjects requiring study drug dose adjustments, undergoing concomitant ITP medication reduction or those who receive rescue therapy during the Extension Phase are required to return for weekly visits for 3 consecutive weeks.

b: This column details the minimum assessments required for those subjects who need an unscheduled visit for dose titration or additional platelet count blood draws, however additional assessment may be performed as required based on other reasons for the unscheduled visit.

c: Visits should occur within a +/- 7-day timeframe.

d: Physical exams, central labs and pregnancy tests will be performed every 3 months starting at Month 1 (Months 1, 4, 7, 10, 13, 16, 19, 22) and EOT.

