13.4.1 Vital Signs Tests and Change from Baseline by Visit

Population: Safety Set

Target Phases: Core Phase, Extension Phase

Visits:

- Core Phase: Baseline, Visit 3 (Day 5), Visit 4 (Day 8), Visit 5 (Week 2), Visit 6 (Week 3), Visit 7 (Week 4), Visit 8 (Week 6), Visit 9 (Week 8), Visit 10 (Week 10), Visit 11 (Week 12), Visit 12 (Week 14), Visit 13 (Week 16), Visit 14 (Week 18), Visit 15 (Week 19), Visit 16 (Week 20), Visit 17 (Week 21), Visit 18 (Week 22), Visit 19 (Week 23), Visit 20 (Week 24), Visit 21 (Week 25), Visit 22 (Week 26), Dose Tapering (Week 1), Dose Tapering (Week 2), Dose Tapering(Week 3), Dose Tapering (Week 4), Follow-up (Week 1), Follow-up (Week 2), Follow-up (Week 3), Follow-up (Week 4)
- Extension Phase (Visit): E 1 (Month 1), E 2 (Month 2), E 3 (Month3), E 4 (Month 4), E 5 (Month 5), E 6 (Month 6), E 7 (Month 7), E 8 (Month 8), E 9 (Month 9), E 10 (Month 10), E 11 (Month 11), E 12 (Month 12), E 13 (Month 13), E 14 (Month 14), E 15 (Month 15), E 16(Month 16), E 17 (Month 17), E 18 (Month 18), E 19 (Month 19), E 20 (Month 20), E 21 (Month 21), E 22 (Month 22), E 23 (Month 23), E 24 (Month 24)

Analysis items:

- For the parameters to be analyzed, refer to Table 2 in [13.4 Vital signs](#)

Contents: - Summary statistics of actual value and change from baseline of vital signs tests at each visit are calculated.

14 Listings

- 16.2.1.1 Subject Disposition (Core Phase and Extension Phase, FAS of Core Phase)
- 16.2.1.2 Screen Failure Subjects (Screen Failures)
- 16.2.2 Subjects with Protocol Deviation (Core Phase and Extension Phase, FAS of Core Phase)
- 16.2.3 Analysis Populations (Core Phase and Extension Phase, FAS of Core Phase)
- 16.2.4.1 Demographics and Baseline Characteristics (SAF of Core Phase)
- 16.2.4.2 Medical History (SAF of Core Phase)
- 16.2.4.3 Surgical History (SAF of Core Phase)
- 16.2.4.4. ITP History (FAS of Core Phase)
- 16.2.4.5 Prior and Concomitant Medication (Core Phase and Extension Phase, SAF of Core Phase)
- 16.2.4.6 Concomitant Procedures (Core Phase and Extension Phase, SAF of Core Phase)
- 16.2.4.7 Concomitant ITP Medication (Core Phase and Extension Phase, SAF of Core Phase)
- 16.2.4.8 Rescue Therapy (Core Phase and Extension Phase, SAF of Core Phase)
- 16.2.5.1 Study Drug Administration (Core Phase, SAF of Core Phase)
- 16.2.5.2 Dosing Regimen Log (Core Phase and Extension Phase, SAF of Core Phase)
- 16.2.5.3 Study Drug Accountability (Core Phase and Extension Phase, SAF of Core Phase)

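### After the Extension EOT visit, no platelet count, WHO bleeding grade or general AE enquiry is scheduled for a subject who permanently stops avatrombopag for an AE or by choice

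*Protocol*

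**What the plan says.** Protocol 5.3.1 covers permanent discontinuation in both phases, including stops for safety and at the subject's request. Its visit requirement is: "If possible, a subject who discontinues treatment will complete the EOT assessments for the applicable phase and protocol-specified information will be collected". For an AE stop it also asks the Investigator to try to follow that event to resolution or stability.

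Protocol 4.4 takes Extension entrants out of the Core post-treatment periods: "Subjects entering directly into the Extension Phase will not enter the Dose-tapering and Follow-up Periods of the Core Study". The last scheduled Extension visit is "Visit E24/Month24: End of Treatment" (7.3.2). It includes a platelet count, the WHO bleeding scale and AE review. After it, 7.3.3 offers only an unscheduled visit.

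For Core subjects who decline the Extension, 4.3.6 sets four weeks of follow-up after the last taper dose and gives the reason: "Platelet counts will be carefully monitored during this period for the recurrence of thrombocytopenia".

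Within the Extension, subjects with a dose adjustment or a concomitant ITP medication reduction, "or who receive rescue therapy during the Extension Phase are required to return for weekly visits for 3 consecutive weeks" (7.3.1).

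On reporting, Protocol 9.1 documents AEs until the subject is discharged from the study. Once the subject has completed or discontinued, 9.4.1 asks only for SAEs that the Investigator learns of and judges related.

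**The concern.** The protocol treats stopping this drug as a period of risk. It schedules counts after the last dose in the Core Phase, and 4.3.5 and 4.3.6 tell the Investigator to consider adding ITP medication then. The same drug is stopped in the Extension, where no equivalent period is written.

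The Extension's primary objective is long-term safety and tolerability. Thromboembolism and WHO Grade 3-4 bleeding are AESIs. If platelets fall after an Extension stop, a resulting bleed may occur after the last contact the protocol schedules. A new non-serious AE, or an SAE not judged related, that occurs after discharge from the study has no route into the safety record. A dose adjustment brings three weekly visits, while a permanent stop for an AE or by choice names none after EOT.

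**Working it through.** The plan has no power or alpha figure on this point, so the check is a count of scheduled visits after the last dose and a comparison of reporting windows.

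**Scheduled checks (platelet count, WHO grade, AE review)**
- Core subject declining the Extension (4.3.6, 7.2.7): Visits 27 to 30, so 30 − 27 + 1 = 4 weekly visits, covering 4 × 7 = 28 days after the last dose.
- Extension subject with a dose adjustment, ITP medication reduction or rescue (4.4, 7.3.1): 3 weekly visits, 3 × 7 = 21 days.
- Extension subject stopped under Table 2 of 6.4.4: the table lists "Discontinue Avatrombopag" in its column of dose adjustments and actions. Whether that triggers the three-visit rule is open, so 0 or 3.
- Extension subject stopping for an AE or by choice: neither reason is among the triggers for weekly visits, and no visit after EOT is named, so 0 after EOT.

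**If stoppers were kept on the monthly schedule.** The text neither requires nor excludes this. Taking 30.4 days per month, 28 / 30.4 = 0.9, or about one visit in the span where the Core has four.

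**Time from last dose to EOT.** None is stated. EOT can fall after the last dose and so supply one off-drug check. As an assumption only, suppose EOT is held at the next monthly visit. Appendix B says "Visits should occur within a +/- 7-day timeframe". The shortest gap is 0 days. The longest arises when one visit is 7 days early and the next 7 days late: 30.4 + 7 + 7 = 44.4 days.

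**Windows side by side**
- AEs (9.1): to discharge from the study, with no fixed time after the last dose.
- Pregnancy (9.5): 30 days after discontinuing study drug.
- Core concomitant medications (SAP 10.3): 30 days after the last dose. Extension concomitant medications (SAP 10.3): to the last treatment day.
- TEAEs (SAP 13.2): events emerging during treatment, with no stated end date, and only TEAEs are tabulated.
- A fourth weekly visit at Day 28 with the ±2-day window for weekly visits (Appendix A, note d) ends at 28 + 2 = Day 30, the same length as 9.5.

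**The case against.** The strongest reply is that such subjects are not abandoned. Protocol 5.3.1 follows the AE that led to the stop, 9.1 follows clinically significant laboratory values, 9.4.2 follows SAEs until they subside or stabilise, and 7.3.3 allows unscheduled visits with all three assessments. This stands, and a reader who inferred that there is no follow-up at all after a stop would be wrong. But these provisions depend on a known event or a perceived need. They do not schedule a look for a new bleed or a falling count, and the 5.3.1 AE provision does not reach a stop by choice.

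Second, the protocol separates stopping drug (5.3.1) from leaving the study (5.3), and SAP 9.2 reports the two separately. Section 7.3.1 asks for monthly visits with drug dispensed only if applicable. A stopper might therefore stay on monthly visits. That is a fair reading, so zero contact is not settled. What is settled is that no visit after EOT is named.

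Third, the comparison is not like for like: Core subjects who decline the Extension are set against Extension subjects who stop early. This also stands. The Core group shows what the protocol considers adequate after the last dose; it is not a matched comparator. Nor does a proven gap follow for early Core stoppers. Sections 4.3.5, 7.2.6, 7.2.7 and Appendix A note b can be read to include them in taper and follow-up, while 4.1, 4.3.4 and 5.3.1 point to completers or to EOT only.

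Fourth, a reader might infer from SAP 10.3 that ITP drugs started after an Extension stop go unsummarised. They are left out of that table, but SAP 11.3.9 counts new ITP medication as rescue with no cut-off at the last dose, so use recorded during the Extension is counted there.

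**Conclusion.** The point holds as a cheap improvement to safety follow-up. For an Extension subject who permanently stops for an AE or by choice, the plan names no platelet count, bleeding grade or general AE enquiry after EOT and leaves the timing of EOT open. Core subjects who decline the Extension have four such checks over 28 days. In a phase whose primary objective is safety, following the plan as written could miss bleeding or thromboembolic events after withdrawal of the drug.

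The size is limited. About 19 subjects are planned and no stopping rate is given, so the number of missed checks or events cannot be stated. The 0 to 44 day range for EOT rests wholly on the assumption that EOT waits for the next monthly visit. The primary endpoint is not affected, because it is confined to the 26-week Core treatment period.

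**What to change.** 1. In Protocol 9.1 and 9.4.1, collect all AEs, AESIs and SAEs, regardless of causality, until 30 days after the last dose, matching 9.5. Put the same window in the SAP 13.2 TEAE definition so that these events are tabulated.
2. In Protocol 7.3.2 and Appendix B, add weekly visits for four weeks after the last dose, with the Visit 27-30 platelet count, WHO bleeding scale and AE review. They apply to Extension subjects who permanently stop, do not continue on commercial avatrombopag and have not withdrawn consent. An EOT visit held after the last dose counts as that week's visit. In the SAP, summarise these visits apart from on-treatment Extension visits; SAP 11.3.3, 11.3.4 and 11.3.11 run to the last visit and would otherwise mix the two.
3. As a wording clarification only, say in 5.3.1 whether Core subjects who stop before Week 26 enter the Follow-up visits.

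No change to the primary endpoint rules or to the Core taper is called for. The cost is a protocol amendment, a few SAP sentences and up to four short visits per stopper, using assessments already in the schedule. Some stoppers will decline them.
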